4.2.1 Duration of the nurse survey

The survey will be administered over a 8 month period between March 2020 and October 2020. This information will be stored and matched with administrative data for up to thirty years, but will not involve any additional follow-up with the nurses.

4.3. Indicate the total number of participants (if applicable, distinguish between the number of participants who are expected to be screened and enrolled, and the number of enrolled participants needed)

Over the four year period, NFP expects to screen 26,000 applicants for eligibility and enroll 6,000 of those into the study; approximately 4,000 will be randomly assigned to the treatment group and 2,000 to the control group.

4.3.1. Total number of participants in the nurse survey.

Over the 6 month period we plan to survey up to 200 nurses.

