The impact estimate is the regression-adjusted difference between the average outcomes of treatment group participants and control group participants. Impact estimates with p-values less than 0.05 (two-tailed test) will be considered statistically significant and provide evidence that there are likely true differences between the groups as a result of NFP.

In addition to these impact estimates, we will also report the percentage of treatment group participants who reported living in a low-income zip code (LIZC) at the time of study enrollment. (LIZC is defined as a zip code in which fifteen percent (15%) or more of households have incomes below the federal poverty guidelines according to 2012 Census Bureau Data.) Before reporting this percentage, we will use Google Map’s Application Programming Interface (API) to confirm that the participant’s self-reported zip code corresponds with their self-reported street address. To do this, we will send a file of unformatted, raw street addresses, cities, and states to Google’s API to return formatted addresses, including zip code. We will then compare these formatted zip codes to the zip codes reported by each study participant. The file we send to Google Map’s API will include a greater number of ‘fake’ (i.e. non-study participant) addresses than actual addresses, to maintain study participants’ confidentiality.

We will also analyze how the main impact estimates vary within our sample. In particular some mothers and their children may be at higher risk for adverse outcomes such as preterm birth or childhood injury. We will define “risk” based on poverty rate in the census tract in which a mother is enrolled. In order to perform this analysis, we will match participants’ self-reported addresses to census tracts in two ways. First, we will send a de-identified file that will only include a randomly generated ID number and the following address information of unformatted, raw street addresses, cities, states, and zip codes to the United States Census Bureau’s Geocoder tool as well as to the geocoding service, Geocodio. We will match addresses to census tracts using both the Census Bureau Geocoder tool as well as Geocodio in order to be able to cross validate the accuracy of the census tract mapping. Mapping to the wrong census tract or failing to map to a census tract will reduce the accuracy of our analysis. The randomly generated ID number will allow for linking census tract

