5.2. Is there a sample size/power calculation?

Yes: If yes; describe the calculation and the scientific rationale, and, if applicable, by site and key characteristics such as participant demographics

NFP plans to serve 4,000 families in South Carolina between January 2016 and January 2020. Our power analysis suggests that with 4,000 families served in the treatment group, we will need a 2:1 T:C ratio (or 2,000 control group families) to achieve 80% or higher chance of detecting statistically significant effects on two out of the three primary outcomes (pre-term birth, birth spacing, and childhood injury), if the true effect size of the outcomes equals the expected effect size provided by NFP. These expected effect sizes are based on analysis of previous NFP trials and baseline knowledge on the current population of South Carolina's Medicaid-eligible first-time mothers and the assumptions summarized below.

As of May, 2015, the expected effective sizes, in percentage difference between the treatment group and the control groups, is -20% for the measure of pre-term birth, -18% for the measure of birth spacing, and -13% for the measure of child injury. In addition, we need 95% or more of women randomized into the treatment group to receive NFP services, and at most 5% of the control group that receives a home visiting program that has as much impact as NFP. Furthermore, our power calculation is based on the assumption that the distribution of the outcomes variables have the following mean (standard deviation) combinations in the absence of NFP intervention: 0.12 (0.32) for the binary measure for pre-term birth, 0.14 (0.34) for the binary measure of birth spacing, and 0.18 (0.30) for the measure of child injury.

With this set of assumptions, we need to enroll at least 6,000 women into the evaluation with a 2:1 treatment to control ratio to achieve near 80% or higher power. With these numbers we will have roughly 70% power to detect a statistically significant effect on the birth-spacing measure if the true effect size is -18%. We will have a nearly 100% chance to detect a statistical significant effect on the child injury measure if the true effect size is -13%. We will not have sufficient statistical power to detect the expected effect (-20%) on the pre-term birth measure; the minimum detectable effect size with 80% power for the pre-term birth measure is -30%.

6. Recruitment Methods

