#### Antenatal health

- Smoking cessation during pregnancy [vital records data]
  - We will consider an enrollee to have ceased smoking during pregnancy if their vital record indicates that they smoked pre-pregnancy and that they did not smoke during pregnancy.
- Recommended gestational weight gain [vital records data]
  - Gestational weight gain will be classified as “recommended” if it is within the guidelines published by the National Academy of Medicine (formerly the Institute of Medicine).

The guideline-recommended antenatal care services should be received at the appropriate gestational age during the pregnancy. The gestational age at the time of the test will be calculated as the date of the test minus the approximate date of last menstrual period (in days). We will approximate the enrollee's date of last menstrual period using the child's date of birth and obstetrician's estimate of gestational age at delivery from the vital records. If these fields are missing, we will define the approximate date of last menstrual period as the beginning date of the index pregnancy (defined above).

Each of these outcomes can only be measured among pregnancies that reach the gestational age at which the care is recommended. The main analyses will only include pregnancies that last at least as long as the gestational age recommended for each outcome. However, it is possible that NFP has a direct effect on gestational age, which would mean that the sample of mothers observed could differ across treatment and control arms. If that is the case (i.e., if gestational age at birth between treatment and control group is statistically significantly different), then we will conduct a bounding exercise as a robustness check for the guideline-concordant care outcomes. Using Group B Strep as an example, the main analysis will compute the average treatment effect (ATE) among people whose pregnancies last at least 35 weeks. If gestational age is statistically significantly different between control and treatment arms, we will estimate two bounds on this ATE: (1) a recalculated ATE assuming *all* people who

did not reach 35 weeks' gestation would have received the test, and (2) a recalculated ATE assuming *none* of the people who did not reach 35 weeks' gestation would have received the test.

Table 1.3. Codes for analyses of antenatal care utilization and quality

	CPT/HCPCS	NDC	ICD-10

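### Bounds for guideline-recommended antenatal care should be reported in all cases, not only when gestational age differs significantly between arms

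*SAP*

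**What the plan says.** SAP Addendum 1 (Antenatal Care Utilization & Quality) lists four guideline-recommended services with gestational windows: anatomy scan at 18-22 weeks, gestational diabetes test at 24-28, Tdap vaccine at 27-36 and Group B strep test at 35-38.

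Under Antenatal health it sets the sample: "The main analyses will only include pregnancies that last at least as long as the gestational age recommended for each outcome". It then concedes that the programme might act on gestational age itself, so that the women observed could differ by arm. The response is conditional. The trigger is worded "if gestational age at birth between treatment and control group is statistically significantly different", and only in that event does the plan commit to any check on the selection, which it describes in these terms: "then we will conduct a bounding exercise as a robustness check for the guideline-concordant care outcomes". The condition is repeated in the Group B strep example: "If gestational age is statistically significantly different between control and treatment arms, we will estimate two bounds on this ATE". One bound counts every woman who fell short of 35 weeks as tested; the other counts none of them.

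The text names no test, no summary of gestational age and no significance level for this trigger. I found no unconditional check on this selection elsewhere in the SAP.

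**The concern.** Reaching the window happens after randomisation, so the main comparison is between groups that randomisation no longer protects. The only planned check is switched on by a significance test, which is a weak switch for two reasons.

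- A non-significant difference is not evidence of comparability. The SAP accepts this for Medicaid coverage. In Addendum 1 (Maternal utilization of mental health services) and in sections 2.5 and 3.5, it says that equal average enrolment would not settle the matter, because the kind of woman or child retained could still differ. It therefore compares baseline characteristics anyway. The antenatal passage does not follow that standard.
- Selection works through the share of each arm that reaches 18, 24, 27 or 35 weeks. Gestational age at birth as a whole is a different quantity and may reflect that share poorly.

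What is at stake is interpretation. If no bounds appear, a reader cannot tell an absence of selection from a trigger with too little power. Group B strep testing is a secondary outcome (Addendum 4, Table 4) and one of four components of the summary index in Addendum 1, section 1.7.

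**Working it through.** **Inputs from the documents**
- Index births: 3,295 and 1,637 (Addendum 4, Table 3).
- Significance level, Protocol section 5.1: "Impact estimates with p-values less than 0.05 (two-tailed test) will be considered statistically significant". I apply it to the trigger, for which the SAP states no level.
- Planned size, Protocol section 4.3: "approximately 4,000 will be randomly assigned to the treatment group and 2,000 to the control group".
- Preterm birth, Protocol section 5.2: control mean and SD "0.12 (0.32) for the binary measure for pre-term birth"; the expected effect "is -20% for the measure of pre-term birth".

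**Assumed, because the documents give no figure:** SD of gestational age, share delivering before 35 weeks, and test uptake.

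**Nearest figures in the plan.** The plan gives no power for the trigger. The Protocol's birth-spacing power reproduces. With dilution 0.95 - 0.05 = 0.90, the effect is 0.14 x 0.18 x 0.90 = 0.0227 and the SE is 0.34 x sqrt(1/2000 + 1/4000) = 0.0093, so power is 68% against roughly 70% stated. The preterm minimum detectable effect of -30% does not: 2.80 x 0.32 x sqrt(1/2000 + 1/4000) / 0.12 = 20.5%, or 22.7% with dilution. That is a separate Protocol matter and no support for this point.

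**Trigger as a test of the mean**

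SE = SD x sqrt(1/3295 + 1/1637) = SD x 0.03024. At SD 2.0 weeks this is 0.0605 weeks. With d the true difference, power = Phi(d/SE - 1.96) + Phi(-d/SE - 1.96).

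| True difference (weeks) | Check runs | Check skipped |
|---|---|---|
| 0.05 | 13% | 87% |
| 0.10 | 38% | 62% |
| 0.12 | about 50% | about 50% |
| 0.15 | 70% | 30% |
| 0.20 | 91% | 9% |

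The 50% point moves from 0.11 to 0.18 weeks as the SD goes from 1.8 to 3.0.

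**Trigger as a test of the share reaching 35 weeks**

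Assume 6% of controls deliver before 35 weeks and a 20% reduction, so 6.0% against 4.8%. SE = sqrt(0.06 x 0.94/1637 + 0.048 x 0.952/3295) = 0.695 points, z = 1.2/0.695 = 1.73, power 41%. Testing the right quantity would not rescue the switch.

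**At the Protocol's expected -20% preterm effect**
- Test of preterm proportions, 12% against 9.6%: (2.4 - 1.96 x 0.923)/0.953 = 0.62, where 0.923 and 0.953 points are the pooled and unpooled SEs. Power is 73%, so 27% are skipped.
- Taking the stated -30% at 80% power at face value: implied SE = 0.30/2.80 = 0.107, z = 0.20/0.107 = 1.87, power 46%, so 54% are skipped.
- Simulation of mean gestational age (2,000 trials per scenario; assumed 12% preterm, SD about 2 weeks): mean difference about 0.12 weeks, 50% skipped. The same simulation gives 85% skipped at -10% and 17% at -30%.

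**Size of the bias, Group B strep**

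Assume 95% of controls reach 35 weeks, the programme moves 1% more past it, 80% of the other women are tested in either arm, and a proportion r of the extra women are tested. With no true effect among the others:

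bias = (0.95 x 0.80 + 0.01 x r)/0.96 - 0.80

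- r = 0: -0.83 points
- r = 40%: -0.42 points
- r = 60%: -0.21 points
- r = 80%: 0

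SE of the main estimate = sqrt(0.8 x 0.2) x 0.03024 = 1.21 points.

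In the same scenario the SAP's bounds, in points, are r - 1 (all counted as tested) and r (none counted as tested), with r as a fraction. That gives -1.0 to 0.0 at r = 0 and -0.6 to +0.4 at r = 40%.

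Wider assumptions (2% to 8% of controls delivering before 35 weeks, reductions of 10% to 20%, 60% or 90% uptake otherwise) put the extreme shift at about 0.1 to 1.5 points. The top figure needs 8%, a 20% reduction, 90% uptake and none of the extra women tested: 1.6 x (-0.90)/0.936 = -1.54.

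**The case against.** The best defence is that little hangs on this.

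- In the main scenario both the bias and the bounds stay within one SE of zero, so the missing table would change no conclusion. The SE of 1.2 is itself too small, because these outcomes also drop women unmatched to Medicaid claims and pregnancies that end before the window. This stands, and it limits the severity.
- Low uptake among the extra women is a pessimistic choice. Women carried several weeks past 35 would have time to be tested, and at equal uptake the bias is zero. This also stands, and is why the range starts at 0.
- The SAP does not say that the trigger tests the mean. True: the skip rates for the mean rest on that assumption. Leaving the test open makes the rule no safer.
- Preterm and extremely preterm birth are compared by arm regardless (Addendum 1, Secondary Outcomes), and nothing forbids reporting the bounds anyway. Readers will therefore see some evidence on early delivery. But the cut-offs of 37 and 28 weeks are not those that define these samples, and the stated rule commits to bounds only after a significant result.
- Earlier windows should be less exposed, since few index births would end by 18 or 24 weeks (the documents give no share). No primary outcome is involved, and Tdap is exploratory in Addendum 4, Table 4.

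None of this justifies the condition. Narrow bounds are worth printing because they reassure.

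**Conclusion.** The rule is unsound as written, with modest consequences. Non-significance does not establish that the women reaching each window are comparable, and the quantity tested is not the one that drives selection. For modest true effects, below about 0.12 weeks in the mean at SD 2.0, the check is more likely to be skipped than run. The likely bias is confined mainly to Group B strep and, under the main assumptions, is below one SE.

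A reader might infer that the check would be skipped in most trials where the samples truly differ. The documents do not support that: they give no SD, no share reaching 35 weeks and no named test, and the answer turns on the true effect. At the Protocol's expected preterm effect the skip rate is 27% to 54% depending on test and inputs; for larger effects the check usually runs. Nor do the documents show that the antenatal results are materially biased. The extreme shift of 1.5 points arises only when every assumption is set unfavourably.

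**What to change.** In Addendum 1, Antenatal health, delete the significance condition in both places where it appears. State that the two bounds already specified will be reported for every guideline-recommended outcome in all cases, beside the number and share of each arm that reached that outcome's gestational window. The construction of the bounds and the main analysis stay as they are.

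The cost is one SAP sentence and one extra table, with no new data. It also removes a reporting decision that depends on the results.

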#### Maternal utilization of mental health services

Analyses of outcomes related to maternal utilization of mental health services is also planned as a stand-alone analysis. NFP guidelines require nurses to screen for depression and anxiety at pre-specified intervals throughout the program, and to follow their agencies' protocols for referral and care coordination for women who screen positive. While directly measuring the

prevalence of depression and anxiety in our study sample would help us assess the impact of NFP on mental health, our study design relies exclusively on administrative data sources for outcome measurement. Therefore, our study design will seek to analyze how NFP changed the utilization of mental health services during the perinatal period.

We include all women with an index birth in our analytic sample, regardless of whether they had a prior mental health diagnosis before pregnancy. Because few women in our study are enrolled in Medicaid prior to pregnancy, we cannot observe prior diagnoses or identify treatment initiation. However, we expect rates of prior mental health diagnoses before pregnancy to be equal across treatment and control arms. Because the outpatient mental health treatment outcomes rely exclusively on Medicaid claims, we will restrict the analytic sample for outpatient outcomes to those women who retain full Medicaid coverage through 60 days postpartum. We will not restrict the sample for inpatient mental health outcomes as these rely on utilization that will be observable in all-payer hospital discharge data, regardless of payer.

While the medical definitions for depression and anxiety are distinct, we examine them together because they are comorbid conditions and NFP screens for them simultaneously. We define outpatient mental health treatment as a composite outcome of either a diagnosis for depression/anxiety/stress reaction or a filled prescription for antidepressants/anxiolytics or an outpatient psychotherapy visit during pregnancy or the first 60 days postpartum. We list the ICD-10 diagnosis codes, therapeutic class codes, and Current Procedure Terminology (CPT) codes used to define these outcomes in Tables 1.4, 1.5, and 1.6. Consistent with prior research, we consider all outpatient psychotherapy visits, including individual, family or group therapy to be mental health visits.

Table 1.4. Diagnosis codes for depression/anxiety/stress reaction

Code description	ICD-10 Code(s)
Depression	F53; O906; F99; O9934*; F32*; F33*
Anxiety	F41.*
Stress-reaction	F43.*

Table 1.5. Therapeutic class codes for filled antidepressants or anxiolytics

Code description	Therapeutic class codes
Antidepressants	281604

Anxiolytics	2824*
-------------	-------

Table 1.6. Outpatient psychotherapy codes

Code description	CPT codes
Psychotherapy (individual, family or group)	90804-90815; 90832-90834; 90836- 90840; 90845-90847; 90849; 90853; 90857; 90862; 90875; 90876

We will also look at these outpatient measures individually (i.e., diagnosis, filled prescription, and psychotherapy) and in combination to enhance our understanding of treatment patterns. For example, we may be interested in the proportion of mothers who receive a diagnosis but do not fill a prescription or receive psychotherapy as this could signal structural or individual-level barriers to treatment. We may also be interested in the proportion of women who receive medication only, as psychotherapy is often recommended as a first-line treatment for mild or moderate depression and in combination with medication when the depression is severe. We may also explore the timing of outpatient mental services (measured in days). NFP could lead to earlier treatment of perinatal depression/anxiety through regular screening, coordinating care, providing a warm hand-off, or by reducing the stigma surrounding mental health and treatment.

For most of the outcomes related to outpatient mental health treatment, we restrict the measurement period to pregnancy through 60 days postpartum because these outcomes are derived from Medicaid claims data and maintenance of coverage past 60 days may be affected by participation in NFP. However, depression and anxiety can take longer than 60 days to manifest, and even longer for the mother to access healthcare. In future analyses, we will consider measuring outpatient mental health treatment patterns through 6, 12 and 24 months postpartum if treatment and control group members are equally likely to be enrolled in *full-coverage* Medicaid plans through these time points.

In our clinical trials registry, we defined a measure of mental health treatment follow-up care as: a second antidepressant prescription or outpatient mental health visit within 120 days of the initial treatment ("acute phase"). However, as noted above, differential Medicaid coverage rates between the treatment arms after 60 days postpartum may preclude us from measuring the treatment effect for this outcome reliably. For example, if treatment group members are more likely to be enrolled in Medicaid after 60 days postpartum than control group members, observed differences in mental health treatment patterns between the treatment and control groups could be due to group differences in the composition of who remains on Medicaid.

To assess whether attrition from full-coverage Medicaid plans affects the comparability of the treatment and control groups, we will assess overall attrition and differences in attrition between the treatment and control groups at the following time points: 60 days (for our main outpatient mental health treatment outcomes), 6 months, 12 months and 24 months postpartum (for other potential measurement periods of interest). We do not consider enrollment in partial-coverage Medicaid plans (such as Family Planning) since these plans cover mental health screenings, but do not reimburse for medications or psychotherapy. Specifically, we will compare partial and continuous enrollment rates in full coverage plans between treatment and control groups at each time point. Continuous coverage will be measured using Medicaid enrollment data and will be defined as enrollment during all months, starting with the month of childbirth through 60 days, 6 months, 12 months and 24 months postpartum. It's possible that while average Medicaid enrollment will not differ between the two groups, the type of women retaining coverage could be affected by NFP. Therefore, we will also test whether the treatment and control group members who remain in the analytic sample at each time point are similar on important baseline characteristics using a joint F-test.

For inpatient mental health outcomes, we will use hospital discharge data to measure mental health related visits on both the extensive and intensive margins. Specifically, we will create an indicator for any mental health related emergency or inpatient visits during pregnancy or the 12 months postpartum based on all-listed diagnoses (i.e. primary or secondary) for depression/anxiety/stress reaction, excluding inpatient claims on the day of delivery. We will also create a count variable for the number of mental health related emergency or inpatient visits during pregnancy or the 12 months postpartum based on all-listed diagnoses for depression/anxiety/stress reaction, excluding inpatient claims on the day of delivery. We examine these hospital-related outcomes because public insurance pays for six of every ten inpatient stays related to mental health, and they could indicate inadequate outpatient treatment for perinatal depression and anxiety. We may also look at diagnoses for depression/anxiety/stress on the day of delivery, as prior research has found that a large proportion of women have diagnoses on this day. These diagnoses may represent cases where women had subclinical or previously unidentified symptoms during pregnancy that were identified during the hospital stay. Finally, we may construct an outcome that captures the proportion of women who have an emergency or inpatient stay related to mental health without any medication or outpatient psychotherapy treatment during pregnancy or the 12 months postpartum.

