4.4. List inclusion criteria

Eligibility Criteria	Process for assessing criteria
Female	Applicant's self-report
No previous live births	Applicant's self-report
Currently pregnant	Applicant's self-report of having received a positive pregnancy test
Gestation period less than 28 weeks (i.e. less than or equal to 27 weeks, 6 days)	Estimated due date; best guess of practitioner and applicant
Ages 15-55	Applicant's self-reported date of birth
Income level meets Medicaid eligibility criteria	Applicant's self-report, verify enrollment and/or eligibility in QuickChecks (State eligibility determination program)
Live within an area serviced by a NFP Implementing Agency	Applicant's self-report of current mailing address
Not currently enrolled in the study	Search for matches by last name & DOB in the study database
Not incarcerated or living in lock down facilities	Applicant's self-report or as reported by the relevant agency or facility

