### Antenatal Care Utilization & Quality

Analyses of outcomes related to antenatal care utilization and quality is planned as a stand-alone analysis. We will examine three groups of outcomes related to antenatal care utilization and quality: utilization of health care services during pregnancy, guideline-recommended antenatal care, and indicators related to antenatal health. We list the outcomes that fall under each area, and their associated data sources, below. We also include the CPT/HCPCS, NDC (National Drug Code) and ICD-10 codes used to identify the outcomes that use Medicaid claims or hospital discharge data in Table 1.3.

The primary sample for this analysis will be mothers with an index birth. We will use vital records, hospital discharge, and Medicaid claims data for the analyses. Mothers who do not match to one of these data sources will not be included in the sample for the corresponding outcomes (e.g., mothers who do not match to Medicaid claims will not be included in the analyses of guideline-recommended antenatal care).

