### **3.5. Endogeneity of Outcome Data and Sensitivity Analyses**

Because outcomes related to contraceptive uptake will rely primarily on Medicaid claims data, we cannot observe contraception use in outpatient settings among women who are not enrolled in Medicaid. As a non-expansion state, all women with Medicaid pregnancy coverage in South Carolina, except undocumented and recent immigrants, retain Medicaid coverage for at least 60 days following childbirth. Women who qualify for other payment categories (e.g. foster-care, disability), may retain coverage past 60 days. Because NFP may affect maintenance of Medicaid coverage past 60 days postpartum, including maintenance of enrollment in Medicaid Family Planning coverage, we may not be able to observe treatment and control group mothers in the Medicaid claims data at equal rates.

To determine whether continuous Medicaid coverage differs between treatment groups, we will first compare continuous Medicaid coverage of any type (coverage through the low-income families, qualified disabled workers, pregnancy and family planning eligibility pathways), and

family planning Medicaid coverage specifically, between treatment and control groups at the three contraception outcome time points (6 weeks, 12 and 24 months). Continuous coverage will be measured using Medicaid enrollment data and will be defined as enrollment during all months, starting with the month of childbirth through 6 weeks, 12 and 24 months postpartum. It is also possible that while average Medicaid enrollment will not differ between the two groups, the type of women retaining coverage will be affected by NFP. Therefore, using a joint F-test, we will also test whether there are differences in the characteristics of participants between control and treatment groups enrolled in Medicaid during the three-outcome time points (60 days, 12 months, 24 months).

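### For outcomes read only from Medicaid claims in pregnancy, the SAP plans no by-arm comparison of Medicaid coverage before the month of birth

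*SAP*

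**What the plan says.** **Outcomes.** Under Maternal utilization of mental health services (SAP Addendum 1), "the outpatient mental health treatment outcomes rely exclusively on Medicaid claims". The composite counts a diagnosis, a filled prescription or "an outpatient psychotherapy visit during pregnancy or the first 60 days postpartum". Under Antenatal Care Utilization & Quality, Medicaid claims are the listed source for ultrasounds, dental visit, anatomy scan (18-22 weeks), gestational diabetes test (24-28), TDAP vaccine (27-36) and group B strep test (35-38).

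**Samples.** The outpatient mental-health sample is "those women who retain full Medicaid coverage through 60 days postpartum". No start month or minimum coverage in pregnancy is given. The antenatal section states only that, for example, "mothers who do not match to Medicaid claims will not be included in the analyses of guideline-recommended antenatal care".

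**Coverage check.** For mental health, the plan will "compare partial and continuous enrollment rates in full coverage plans between treatment and control groups at each time point". The time points are 60 days and 6, 12 and 24 months postpartum. Continuous coverage is "defined as enrollment during all months, starting with the month of childbirth through 60 days, 6 months, 12 months and 24 months postpartum". A joint F-test on baseline characteristics is run at the same time points. Section 3.5 (contraception) uses a parallel definition, "enrollment during all months, starting with the month of childbirth through 6 weeks, 12 and 24 months postpartum".

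**Entry.** Protocol 4.4 has staff "verify enrollment and/or eligibility in QuickChecks", so enrolment itself is not required. Entry is allowed up to 27 weeks 6 days. The mental-health section adds that enrolment in Medicaid before pregnancy is uncommon in this sample.

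**The concern.** The coverage check should span the period in which the outcome can be recorded. Section 3.5 does this for contraception, which is a postpartum outcome. For the claims-based pregnancy outcomes, the check begins roughly where most of the outcome window ends.

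The SAP accepts in several places that NFP may affect whether coverage is kept after birth, but it does not consider the start of coverage. A woman randomised while eligible but unenrolled has weeks in which care would leave no Medicaid claim. Once she has any matched claim, nothing in the antenatal section removes her or marks those weeks as unobserved. If enrolment then came sooner in the NFP arm, more of that arm's care would be seen. Both arms could be equally covered from the birth month onward, so every planned check could pass while covered pregnancy time differed.

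At stake is the interpretation of secondary and exploratory outcomes, including those carried into the indices in Tables 4 and 8 of Addendum 4. No primary outcome depends on it.

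**Working it through.** The plan gives no figure to reproduce. The check compares observation windows, then illustrates the size.

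**1. Windows**

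| Outcome group | Counted over | By-arm coverage check |
|---|---|---|
| Outpatient mental health | Pregnancy to 60 days postpartum | Postpartum time points; continuous coverage from birth month |
| Six claims-based antenatal services | Pregnancy, or a gestational window | None stated |
| Contraception | Mostly from discharge to 6 weeks, 12 or 24 months | From birth month to 6 weeks, 12 and 24 months |

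**2. Does another part of the SAP fill the gap?**
- Section A.2 says claims-only outcomes are not observed for women outside Medicaid, promises to characterise missingness where possible, and refers to the addenda for detail. Addendum 1 gives none for pregnancy coverage.
- The by-arm categories in section 1.4 are pregnancy loss, linking error and unmatched outcome.
- The antenatal bounding exercise addresses gestational age only.
- The control variables in section B.1 do not include Medicaid status at entry.

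**3. Which windows can NFP affect?** Only coverage gained after randomisation. For a woman entering after 22 weeks, the anatomy-scan window has already closed. For one entering between 24 weeks and 27 weeks 6 days, part of the diabetes-test window has passed. The TDAP and group B strep windows fall almost wholly after randomisation.

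**4. Size, with no true effect on care**

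Inputs: 3,295 and 1,637 mothers with an index birth (SAP Addendum 4, Table 3); two-sided 0.05 (Protocol 5.1). Assumptions not in the documents: control coverage c = 85% when the service is due; true receipt r = 20%, 50% or 80% in both arms; coverage gap g = 1, 2 or 5 points; care while uncovered is equally frequent but unseen.

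Recorded rates are p_C = r × c and p_T = r × (c + g), so the spurious difference is d = r × g.

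Worked case, r = 0.80 and g = 0.05:
- p_C = 0.80 × 0.85 = 0.68; p_T = 0.80 × 0.90 = 0.72; d = 0.04.
- SE = √(0.72 × 0.28/3295 + 0.68 × 0.32/1637) = 0.0139.
- A two-proportion z-test (pooled SE under the null) gives p < 0.05 with probability about 0.83.

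| True receipt | Gap 1 point | Gap 2 points | Gap 5 points |
|---|---|---|---|
| 20% | 0.2 points (5%) | 0.4 (6%) | 1.0 (14%) |
| 50% | 0.5 (6%) | 1.0 (10%) | 2.5 (38%) |
| 80% | 0.8 (9%) | 1.6 (21%) | 4.0 (83%) |

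In brackets: chance of p < 0.05, against a nominal 5%.

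The differences are upper bounds. If coverage enables care, part of the difference is a real effect of the offer. For an outcome spanning the whole pregnancy, a late enrollee can still be recorded from later claims. The chances use every index birth; the Medicaid-matched or 60-day-covered samples may be smaller, which would raise the SE and lower the chances. The ultrasound outcome is a count, so the table applies to it only by analogy.

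**The case against.** The strongest reply is that the mechanism is assumed. No passage says that NFP speeds enrolment in pregnancy; the SAP raises only the keeping of coverage after birth. Enrolment or eligibility is checked in both arms before randomisation, and one recruitment route (Protocol 6.1, item d) starts from women already newly enrolled in Medicaid. Only women unenrolled at randomisation can contribute, and their number is not given. This stands: the point concerns a check that is missing, not a bias that has been shown.

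The text is also looser than it may appear. The birth-month start defines continuous coverage only; partial enrolment is compared too, with no start date. The verb retain in the mental-health sample rule may imply earlier coverage. Both observations are fair, but neither specifies a comparison of coverage in pregnancy. Nor does the SAP say how a matched woman's uncovered weeks are scored. That the absence of a claim counts as no service is an inference from the outcome definitions.

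A reader might infer that all antenatal and mental-health outcomes are affected. They are not. Prenatal care adequacy, smoking cessation and weight gain come from vital records. Emergency department visits, maternal-fetal medicine consultation and mental-health emergency or inpatient visits come from all-payer discharge data.

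A reader might also infer that the main sample should become women enrolled in the month of randomisation. That does not follow: a woman randomised early in a month could be enrolled with a nurse's help later that month. Addendum 4 describes the trial manuscripts as published or forthcoming, so replacing a planned main sample would now be a post hoc change of target population.

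**Conclusion.** The gap is real and limited. For outpatient mental-health treatment and the six claims-based antenatal services, no stated by-arm comparison covers Medicaid enrolment before the birth month, although enrolment can begin after randomisation. The planned checks therefore could not detect a difference in observation during pregnancy.

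Whether such a difference exists is unknown. The stronger conclusion, that recorded care in the NFP arm is inflated, is not supported by the documents. The size rests entirely on assumed coverage gaps and receipt rates. A 1-point gap is nearly harmless, and a 5-point gap in a service with 20% receipt adds little. A 5-point gap in a service most women receive could by itself often produce a significant result. This is a cheap improvement to the analysis of secondary and exploratory outcomes.

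**What to change.** Keep the planned main samples. In Addendum 1:

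1. Extend the by-arm coverage comparison and joint F-test to three further measures: Medicaid start date, covered months from randomisation to delivery, and coverage in each gestational service window.
2. Add a sensitivity analysis of the claims-based pregnancy outcomes in women whose Medicaid enrolment was in place before the randomisation date. If enrolment data are monthly, use the preceding calendar month. NFP cannot influence that status.
3. State that, if coverage in pregnancy differs by arm, these outcomes will be interpreted with caution, as the plan already does for postpartum coverage.

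Addendum 4 states that its analyses had not been performed when it was submitted, so the same check can accompany its indices. For results already published, it would be a labelled post hoc check.

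The cost is one more pass over enrolment files already held (SAP Table 1 uses pregnancy enrolment to identify the index pregnancy). Only the sensitivity analysis has a smaller sample.
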